3.2. Phase 2 Trial Objectives and Endpoints

In phase 2 exploratory trials, the default primary objective for both part A and B is to explore the effect of the intervention on respiratory dysfunction, in line with the RECOVERY platform trial protocol. The same objectives and endpoints as for phase 3 trials should be considered, but the final selection, ranking and frequency of assessments will be given in the intervention-specific sub-protocols according to the intervention and the disease stage at inclusion. In addition, more specific end points should be specified according to the characteristics and mode of action of the IMP, and according to emerging variants of SARS CoV2.

Table 3.2 Phase 2 objectives and corresponding endpoints

Objectives	Endpoints
Primary	
The primary objective is to explore the effect of therapeutic interventions on respiratory dysfunction	SpO ₂ /FiO ₂ -ratio at day 5
Secondary	
Secondary objectives are selected from the objectives in Table 3.1 as relevant for the IMP (based on the mode of action)	Corresponding endpoints are selected from Table 3.1 , possibly with increased frequency of assessment

3.3. Further specification to endpoints

- Disease progression with scores refers to the WHO clinical progression scale as defined in Table 8.1
- Death is death by any cause.
- Home is defined as the level of residence or facility where the participant was residing prior to hospital admission leading to enrolment in this trial (the index hospitalization).
 - Residence or facility groupings to define home are:
 - Independent/community dwelling with or without help, including house, apartment, undomiciled/homeless, shelter, or hotel.
 - Residential care facility (e.g., assisted living facility, group home, other non-medical institutional setting).
 - Other healthcare facility (e.g., skilled nursing facility, acute rehab facility) and
 - Long-term acute care hospital (hospital aimed at providing intensive, longer term acute care services, often for more than 28 days).
 - Lower (less intensive) level of residence or facility will also be considered as home.
 - By definition, “home” cannot be a “short-term acute care” facility. Participants previously affiliated with a “long-term acute care” hospital recover when they return to the same or lower level of care.
 - Readmission from “home” may occur and if this occurs within 14 days of the first discharge to “home”, then sustained recovery will not be reached until such time as the participant has been at home for 14 consecutive days.

- Participants residing in a facility solely for public health or quarantine purposes will be considered as residing in the lowest level of required residence had these public health measures not been instated.
- Hospital discharge is defined as a state without the need for hospitalization. If hospitalized for isolation reasons only, define as discharged.

4. Study Design

4.1. Overall Design

EU-SolidAct is a European, multi-centre, randomized, parallel group, platform trial, exploring and assessing the efficacy and safety of drug interventions, new or repurposed, single or in combination, in hospitalized participants with moderate or severe/critical COVID-19. In case combination treatment evaluations, a factorial design may be applied by adding a combination arm to the two separate single intervention arms. In phase 3 trials, both superiority and non-inferiority hypotheses may be evaluated. In phase 2 trials, only superiority hypotheses will be evaluated.

This master protocol describes the framework for the general study population and the common study elements of the platform trial. The accompanying sub-protocols will present the intervention-specific information, including any intervention-specific objectives and endpoints, details of administration and dose, additional inclusion and exclusion criteria and study procedures. The decision to include a new sub-protocol will be taken in the Trial Steering Committee based on the recommendations from a separate drug evaluation committee.

As available evidence suggests that different drugs may have different efficacy depending on the stage of the disease, EU-SolidAct will be divided into two parts according to disease stage at inclusion:

- EU-SolidAct Part A will include patients with moderate COVID-19 defined as hospitalised patients without oxygen therapy or oxygen by mask or nasal prongs needed (similar to WHO score¹ 4-5)
- EU-SolidAct Part B will include patients with severe/critical COVID-19 (corresponding to WHO score¹ 6-9 and WHO treatment guidelines for dexamethasone²) defined as hospitalised patients fulfilling at least one of the following criteria:
 1. SpO₂ < 90% on room air, or
 2. SpO₂ 90-94% with a downward trend and/or signs of respiratory distress*, or
 3. Need of oxygen by NIV (CPAP, BIPAP), high flow or non-rebreather mask, or
 4. Need of mechanical ventilation/ECMO

*persistently increased respiratory rate, use of accessory muscles, inability to complete full sentences. Clinical judgement must be applied to determine whether a low oxygen saturation is indicative of disease progression or severity or is habitual for a given patient (i.e., with underlying chronic lung disease).

Control treatment:

- The control treatment for superiority trials will be the SoC at the local hospital defined as the best available treatment according to local hospital guidelines. The SoC might change as new treatment evidence emerges. Use of new treatment as part of SoC will be captured in the trial database.
- Placebo plus SoC might be considered as control treatment if available, otherwise open-label SoC will be given against open-label intervention. This will be detailed in the intervention-specific protocol.
- If components of SoC are contraindicated with the study intervention(s), we might consider head-to-head comparisons between the study intervention(s) and the SoC component, either to assess or confirm superiority or non-inferiority. This will be detailed in the intervention-specific protocol.
- Current SoC should include the use of dexamethasone 6 mg/day for 10 days in severe or critically ill patients (Part B). Duration and dose could change according to emerging evidence. Other doses or frequencies might be used at the discretion of the treating physician based on clinical judgement.

4.1.1. Randomization:

Participants in EU-SolidAct will randomly be assigned in an equal ratio between the comparator treatment arm(s) and the available active treatment(s) for which the participant is eligible. Over time, it is expected that SoC will evolve. Thus, randomization will be aligned with the current clinical situation and the incremental effects of the study treatment(s) will be appropriately assessed. The randomization will be stratified as described in section 6.3.

In the case of both open-label and blinded investigations in the same part, participants are still randomly assigned in an equal ratio between the arms they are eligible for. In the example figure below with a participant eligible for all five arms in Part B, first the participant is allocated to either investigation B1 or B2 in a 2:3 ratio, and then to either Active 1 or Placebo 1 in a 1:1 ratio or to Active 2, Active 3 or open-label SoC in a 1:1:1 ratio.

[figure not shown]

Figure 4.1 Randomisation illustration

4.1.2. Comparison(s):

Each study intervention arm will be compared to their concurrent comparator arm. Concurrent comparator arm encompasses participants that were randomized to the comparator arm when the study intervention was available and eligible for randomization. Thus, the same participant can act as comparator for more than one study intervention arm, dependent on hypothesis to be tested. Specifications on appropriate comparator(s) will be given in the intervention-specific sub-protocol. For blinded investigations the comparator will primarily be the matching placebo arm, while for open-label trials the arm with no treatment will be the comparator arm for all interventions. In the case of non-inferiority trials, the comparator will be the active treatment which the intervention will be compared to.

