If one or more of the active drug treatments are not available at the hospital, opted out by the hospital or contraindicated for a specific participant, then this fact will be recorded via the web-based form prior to randomization; random allocation will then be between the remaining arms. If no treatments are available and suitable, the participant cannot be randomized and must be withdrawn from the trial.

This study could include both open-label and placebo-controlled interventions. In the case of open-label interventions, all investigators, site pharmacists, study nurses, sponsor safety staff and participants will be unmasked and aware of the treatment allocation throughout the study. However, they will be unaware of aggregate outcomes during the course of the study.

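### The concurrent comparator in Section 4.1.2 does not require that a control could have been allocated to the drug, so a shared open-label SoC arm can admit controls contraindicated for it

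*Protocol*

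**What the plan says.** Section 4.1.2 of the protocol defines the control group for every comparison: "Concurrent comparator arm encompasses participants that were randomized to the comparator arm when the study intervention was available and eligible for randomization". It then allows sharing, "Thus, the same participant can act as comparator for more than one study intervention arm, dependent on hypothesis to be tested", and fixes the open-label case: "for open-label trials the arm with no treatment will be the comparator arm for all interventions". For blinded work it says "For blinded investigations the comparator will primarily be the matching placebo arm", and it adds that "Specifications on appropriate comparator(s) will be given in the intervention-specific sub-protocol".

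Allocation itself is described participant by participant. Section 4.1.1 randomizes equally between the comparator arm(s) and "the available active treatment(s) for which the participant is eligible". Section 6.3 covers a drug that is not available at the hospital, opted out by it, or "contraindicated for a specific participant, then this fact will be recorded via the web-based form prior to randomization"; in that event "random allocation will then be between the remaining arms".

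The efficacy analysis set in Section 9.2 is everyone randomized. The primary analysis in Section 9.3.2 is a Cochran-Mantel-Haenszel (CMH) difference adjusted for the randomization strata. Table 6.3 lists these as centre plus baseline oxygen need in Part A, and centre, previous entry in Part A and type of respiratory support in Part B. Country may replace centre if strata are too small.

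**The concern.** A concurrent-control comparison is a randomized comparison only if every control had a chance of being allocated to the drug. Sections 4.1.1 and 6.3 apply that condition when participants are allocated. Section 4.1.2 does not repeat it when they are compared: what must be available and eligible there is the study intervention, which reads as a rule about calendar time and arm status.

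The worked example in Section 4.1.1 shows how the gap opens. It has Active 2, Active 3 and open-label SoC at 1:1:1. A participant contraindicated for Active 2 is randomized between Active 3 and SoC. If allocated to SoC while Active 2 is open, that person counts, on the literal reading, as a control for Active 2, whereas the Active 2 arm holds only people who could take it.

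At stake is the validity of the primary comparison for any open-label drug that shares its SoC arm. Contraindications are often conditions with prognostic weight: Section 8 lists kidney disease, liver disease and immunodeficiency among the risk factors for severe COVID-19. Which conditions exclude a participant from a given drug is left to the sub-protocols, so these are illustrations only.

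**Working it through.** **Does anything in the protocol remove these controls?**

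- Full analysis set (9.2): no. It contains all randomized participants.
- CMH strata (6.3, 9.3.2): not for contraindications, because no stratum records eligibility for a drug. For a drug that a hospital lacks or has opted out of, largely yes: a centre with no participants on X contributes nothing to a centre-stratified difference. That protection weakens if country replaces centre.
- Blinded investigations: not exposed. Someone who cannot take the active drug is not entered in that investigation and so cannot receive its matching placebo.

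**The plan's own figure.** Section 9.5.1 gives 924 per arm for 15% against 10%, two-sided 5%, 90% power.

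- HR = ln(0.90)/ln(0.85) = 0.648.
- Freedman events = (1.960 + 1.282)² × [(1 + 0.648)/(1 − 0.648)]² ≈ 231.
- Mean event rate = (15% + 10%)/2 = 12.5%, so N = 231/0.125/2 = 924 per arm.

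This reproduces the stated size. The check below uses the plan's 15% rate and its planned 950 per arm.

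**Size of the bias.** Let q be the share of controls ineligible for X and m their event rate; both are assumptions. There is no true effect, so the drug arm and the eligible controls are at 15%.

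- Control rate: p_c = (1 − q) × 0.15 + q × m
- Bias = p_c − 0.15 = q × (m − 0.15); positive favours the drug
- SE = √[0.15 × 0.85/950 + p_c(1 − p_c)/950]
- Two-sided type I error = Φ(−1.96 + bias/SE) + Φ(−1.96 − bias/SE)

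| q | m | p_c | Bias (points) | SE | Type I error |
|---|---|---|---|---|---|
| 10% | 10% | 14.5% | −0.5 | 0.0163 | 6% |
| 10% | 15% | 15.0% | 0 | 0.0164 | 5% |
| 10% | 20% | 15.5% | +0.5 | 0.0165 | 6% |
| 10% | 25% | 16.0% | +1.0 | 0.0166 | 9% |
| 20% | 10% | 14.0% | −1.0 | 0.0161 | 9% |
| 20% | 25% | 17.0% | +2.0 | 0.0168 | 22% |

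For the last row: 0.020/0.0168 = 1.19, and Φ(−0.77) + Φ(−3.15) = 0.221.

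**From participants to controls.** Ineligible participants are spread over fewer arms, so they are over-represented among the controls. With two open-label drugs plus SoC, if a share f of participants is ineligible for X only, then q = (f/2) / [f/2 + (1 − f)/3]. For f = 5%, 10%, 20% and 30%, q is 7%, 14%, 27% and 39%. Keeping 950 eligible controls and adding the ineligible ones, f = 10% adds 950 × 0.05/0.30 ≈ 158. Type I error is then 7.3% at m = 20% (0.7 points in the drug's favour), 14% at m = 25% (1.4 points), and 7.4% at m = 10% (0.7 points against the drug).

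All of this is crude, without CMH stratification.

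**The case against.** The strongest reply is that the text can be read participant by participant. Each control has their own randomization, and Section 6.3 decides drug by drug which arms are open at that moment. For someone contraindicated for X, X was arguably not eligible for randomization, so Section 4.1.2 may already mean what it should. That reading is possible, but the sentence does not compel it. Section 4.1.1 names the participant's eligibility explicitly and Section 4.1.2 does not.

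Second, comparator specifications are left to sub-protocols, and sharing is worded as something that can happen, depending on the hypothesis. A sub-protocol could therefore close the gap. The master protocol does not tell it to, and this definition governs future arms.

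Third, the reach is limited. The only intervention summarized, baricitinib, is double-blind against its own placebo and is untouched. Centre adjustment largely deals with hospital opt-outs. Both points stand.

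A reader might go further and infer that contraindicated controls certainly enter the primary comparisons, that they raise the control event rate and so favour the drug, and that false non-inferiority claims follow. The documents do not support this. Entry depends on the literal reading, a shared open-label SoC arm and no restriction in the sub-protocol. No event rate for ineligible participants is given, so the direction is open. In non-inferiority trials Section 4.1.2 makes the comparator the active treatment, so bias arising through the SoC arm does not carry over to them.

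**Conclusion.** The concern holds as a conditional defect of definition. Section 4.1.2, applied literally, allows a control who could not have been allocated to drug X into X's primary comparison whenever two or more open-label drugs share an SoC arm. Neither the analysis set nor the stratified analysis removes patient-level contraindications.

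The resulting bias is q × (m − 15%): zero if ineligible participants have the same prognosis, and otherwise in either direction. Over the assumed range in the table it runs from 1.0 point against the drug to 2.0 points in its favour, with two-sided type I error between 5% and about 22%. For scale, the planned effect is 5 points. The shares and event rates are assumptions; only the 15% rate and the 950 per arm come from the protocol.

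**What to change.** Reword Section 4.1.2 so that the concurrent comparator for an intervention comprises participants randomized to the comparator arm for whom that intervention was one of the arms open to allocation at their own randomization: available at the site, not opted out and not contraindicated, as entered on the web form before randomization. State in Section 9.2 that the full analysis set for each comparison is restricted in this way.

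The cost is one sentence in each place. The data needed are already captured under Section 6.3. Some arms will have slightly fewer controls. Because allocation is equal among the arms open to each participant, drug and control remain 1:1 within every eligibility set. If the planned number is counted in eligible controls, 950 against 950 gives about 91% power for 15% against 10% (two-proportion calculation), so the planned size need not change.

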4.2. Scientific Rationale for Study Design

- Due to the high research focus on COVID-19, there are a multitude of treatment hypotheses being generated and in need of being tested in rigorous randomized controlled trials. Platform trials and the set-up of master protocols provide efficient and consistent paths to test new treatments through a common and concurrent control treatment arm, common eligibility criteria and outcome measures.
- While avoiding imminent death is the ultimate goal in hospitalised patients with a potential lethal disease, the incidence is usually much lower in patients with moderate

disease compared to patients with severe or critical disease. Therefore, the EU-SolidAct trial will evaluate interventions separately for moderate and severe/critical disease stages, with separate endpoints, assuming it will be easier to see an effect on disease progression compared to death in moderate disease.

- The master protocol includes a broad range of hospitalised patients, aiming for a wide generalisability of the results.
- The master platform accommodates both exploratory (phase 2) and confirmatory (phase 3) trials, thus encompassing two important phases of drug development in a new indication.
- The concept of combining treatments to optimize clinical effect is not new in infectious diseases.

4.3. Justification for Dose

Justification of dose of each intervention and combination, if applicable, will be given in the intervention-specific sub-protocol.

4.4. End of Study Definition

Participant Completion

A participant is considered having completed the study if he/she has completed all periods of the study including the last scheduled procedure at Day 91 shown in the Schedule of Assessments (SoA, section 1.2). The expected total trial duration for each participant will be approximately 90 days. If longer or shorter duration is warranted to meet the objectives of specific investigations, this will be stated in the corresponding sub-protocol.

Intervention-Specific Completion

The study of a specific intervention is considered completed when the last participant in the intervention cohort has completed all periods of the study including the last scheduled procedure shown in the SoA.

Platform Study Completion

The platform is considered completed when the last intervention-specific study has been completed.

5. Study Population

All participants must satisfy all the inclusion and exclusion criteria in this master protocol to be enrolled in the platform trial. Any additional intervention-specific criteria will be described in the applicable sub-protocol. The eligibility criteria will be considered by the principal investigator or delegated clinical site personnel.

Prospective approval of protocol deviations to recruitment and enrolment criteria, also known as “protocol waivers” or “exemptions”, are not permitted.

The eligibility criteria listed below are quite general and is suited for phase 3 confirmatory trials. In phase 2 exploratory trials, more restrictive criteria might be necessary to accommodate the increased uncertainty and potential risk of the treatment.

5.1. Inclusion Criteria

Participants are eligible to be included in the study only if all the following general inclusion (GI) criteria apply:

GI1. ≥ 18 years of age

GI2. Laboratory-confirmed SARS-CoV-2 infection (new infection or reinfection) as determined by PCR not more than 14 days old.

GI3. Admitted to hospital

GI4. Informed consent by the participant or legally authorized representative

GI5A: Moderate disease state defined as hospitalised patients without oxygen therapy or oxygen by mask or nasal prongs needed, or

GI5B: Severe/critical disease state defined as fulfilling at least one of the following criteria:

1. SpO₂<90% on room air, or
2. SpO₂ 90-94% with a downwards trend and/or signs of respiratory distress*, or
3. Need of oxygen by NIV (CPAP, BIPAP), high flow or non-rebreather mask, or
4. Need of mechanical ventilation/ECMO

*persistently increased respiratory rate, use of accessory muscles, inability to complete full sentences. Clinical judgement must be applied to determine whether a low oxygen saturation is indicative of disease progression or severity or is habitual for a given patient (i.e., with underlying chronic lung disease).

NIV=non-invasive ventilation. CPAP= Continuous Positive Airway Pressure, BPAP= Bi-level Positive Airway Pressure, ECMO = extracorporeal membrane oxygenation.

Additional inclusion criteria are given in the intervention-specific sub-protocols.

5.2. Exclusion Criteria

Participants are excluded from the study if any of the following general exclusion criteria apply:

GE1. Anticipated transfer to another non-trial hospital within 72 hours

Additional exclusion criteria, including prohibited medication, confounding trials and details on contraception and pregnancy are given in the intervention-specific sub-protocols

5.3. Lifestyle Considerations

Included in intervention-specific sub-protocols if applicable.

5.4. Screen Failures

A screen failure occurs when a participant who has consented to participate in the clinical study is subsequently not entered in the study. A minimum set of screen failure information is required to ensure transparent reporting of screen failure participants to meet the Consolidated Standards of Reporting Trials (CONSORT) publishing requirements and to respond to queries from regulatory authorities. Minimal information includes demography, screen failure details, eligibility criteria, and any serious adverse event (SAE).

Individuals who do not meet the criteria for participation in this study (screen failures) may not be rescreened.

5.5. Criteria for Temporarily Delaying Enrolment, Randomization or Administration of Study Intervention

If there are internal or external signs or evidence of harm by any of the study interventions, the randomization to the corresponding treatment arm could be temporarily delayed until further investigations or data analyses resolve the issue. This would be done by continuing the randomization or by permanently removing the intervention from the randomization. The sponsor is ultimately responsible for this decision, but it could be guided by an assessment in the data monitoring committee.

6. Study Interventions and Concomitant Therapy

Study intervention is defined as any investigational interventions, marketed products, or placebo, intended to be administered to a study participant according to the study protocol.

